In recent years lavender has been studied on human subjects to tests its known reputation for sedative, anxiolytic, and analgesic properties. In one clinical trial oral administration of lavender was compared to Ativan 0.5mg for generalized anxiety disorder. The study supported that the oral lavender oil called Silexan was as effective as 0.5mg of Ativan in adults with generalized anxiety disorder [5]. A second clinical trial analyzing sleep quality found that ischemic heart patients in the intensive care unit received better sleep with 100% lavender oil undiluted placed on a cotton ball within 20cm from the patient from the hours of 9pm-6am [6]. Two studies have used lavender oil through inhalation in the recovery room with an oxygen mask after surgery for pain control. The first study was patients after breast biopsy, the second was patients who just had laparoscopic adjustable gastric banding [7,8]. The study with the breast biopsy patients showed a higher satisfaction rate with pain. The patients undergoing laparoscopic banding also showed a higher rate of satisfaction with pain as well as decreased opioid use in the recovery room. Furthermore one study used 100% lavender oil undiluted on the skin of pediatric patients undergoing tonsillectomy as a topical application and asked the patients to inhale. The study showed a decrease use in Tylenol usage postoperatively [9].

4. Design & Procedures:

Design

Randomized study with control group and test group. Using a 1:1 treatment allocation ratio, the total of 60 patients (30 per arm) will be randomly assigned to control or treatment arm. The Statistical Investigator will generate the randomization scheme and monitor the randomization process over the course of the trial. The study will use randomization with random permuted blocks. The test group will receive 50% lavender oil diluted in fractionated coconut oil and the control group will have the current standard of care with no essential oil intervention (coconut oil only) will be applied. Fractionated coconut oil is being used because it is colorless, odorless, does not stain clothing, and has a long shelf life. It also serves as a carrier oil for the essential oil to absorb into the skin instead of evaporating off the skin due to essential oils volatile nature.

Study Procedure

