During surgery the patient will receive 4 drops of 50% solution lavender oil on the temple region over the temporal artery every 2 hours until completion of surgery. This will be applied by the anesthesia team. If the temporal region is not accessible the shoulders or feet will be alternate locations of application. When the patient arrives to the recovery room she will receive lavender oil through an oxygen mask. A 50 % solution will be used by placing 4 drops of the lavender solution on the mask and wiping it around the mask with a cotton ball. This delivery method will be used because this was used in a study from New York University Medical Center studying postoperative pain and no adverse events occurred [7]. When the patient is on the post-operative floor she will receive 50 % lavender oil on the wrist every 4 hours in the same manner as preoperatively from the hours of 6am to 9pm. Nightly (9pm-6am), 8 drops of 50% lavender oil will be placed on the cotton ball situated within 20cm of the patient. This method and concentration was chosen after reviewing a study in ischemic heart patients in the intensive care unit. The patients received lavender at bedside on a cotton ball and had statistically significant better sleep quality [6]. The control group will have coconut oil applied without any lavender oil applied in the same sequence as listed above. This will ensure the same procedures are carried out under both arms.

Blood pressure, pulse, respiratory rate, and oxygen saturation will be monitored in the preoperative area before lavender is given and 30 minutes after it is given. The level of pain will also be asked prior to application and at the second set of vitals. The control group will get two sets of vital measurements and pain scale measurements without any intervention. The same vitals will be recorded while the patient is under anesthesia every 30 minutes. There will be a notation in the chart when lavender is given to correlate time from application to time of vitals recorded. A review of the electronic medical record will be done to record amount of narcotic needed interop in both groups.

In the recovery room after the patient is given lavender through the oxygen mask the same vital signs and pain score measurement will be taken 15, 30, and 60 minutes from lavender application. In the control group on arrival to the recovery room the same data points will be

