measured with the same time intervals with coconut oil only. The amount of narcotic needed in the recovery room will be taken from the electronic medical record for each group.

Postoperatively on the floor vital signs as noted above will be recorded every 4 hours. At each 4 hour interval after the vital signs are taken lavender will be applied to the experimental group and no intervention in the control group. One more set of vitals signs will be recorded 45min after application of lavender each time lavender is applied. There will be a review of narcotic use from the electronic medical record from both groups. There will be a notation when lavender was given to correlate lavender application and narcotic use.

The anxiety questionnaire will be given preop before the application of lavender and then daily for every post-op day they stay. The questionnaire is called the hospital anxiety and depression scale.

The sleep questionnaire will be given in preop before application of lavender and then daily for every post-op day they stay. The sleep questionnaire is called the Richard Campbell Sleep Questionnaire.

Daily starting on postop day 1 the patient will also record their level of satisfaction of pain control from a scale of 1-10 with 1 being not satisfied and 10 being satisfied. Patients typically stay in hospital 1-3 days post-op. A survey will be filled out daily.

10. Risk/Benefit Assessment:

The use of lavender essential oil could have potential benefits to the patient:

- $\circ~$ Main benefits include decreased pain, better sleep, and better mood.
- o Other benefits include relaxation, calming environment, pleasing aroma.

Risks are minimal, but there is potential for some adverse events:

• Possible side effects include skin irritation or coughing.

- If skin irritation occurs, plain fractionated coconut oil will be applied to dilute the essential oil. Then a 4x4 cotton gauze will be used to wipe off the essential oil. The coconut oil will be applied a second time and then removed by a 4x4. Washing is not a recommend step because water will drive the essential oil into the skin further. If there is still a reaction and the patient is uncomfortable oral Benadryl will be given, 25mg PO Q6hrs prn itching or skin irritation. In the control arm, should the coconut oil irritate the skin it will be removed using a 4 x 4 cotton swab.

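### Two sentences give controls no intervention where the plan elsewhere requires coconut oil in the same sequence, and the 45-minute floor vital signs have no stated control timing

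*Combined protocol and SAP*

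**What the plan says.** The general rule is in Section 9 (Study Interventions), after the full list of application steps: "The control group will have coconut oil applied without any lavender oil applied in the same sequence as listed above". Its purpose follows: "This will ensure the same procedures are carried out under both arms". Section 4 (Design & Procedures) describes the control in the same spirit: "no essential oil intervention (coconut oil only) will be applied".

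Three later sentences in Section 9 do not fit cleanly with that rule:

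- Preoperative measurements: "The control group will get two sets of vital measurements and pain scale measurements without any intervention".
- Postoperative floor, at each 4-hour interval: "lavender will be applied to the experimental group and no intervention in the control group".
- Repeat vital signs on the floor: "One more set of vitals signs will be recorded 45min after application of lavender each time lavender is applied". No control timing is given.

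The recovery-room sentence lies between the first two and does name the control oil: control data are "measured with the same time intervals with coconut oil only".

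**The concern.** The application is more than a few drops of oil. Before surgery the patient rubs her wrists and hands together and breathes slowly for one minute, and the daytime floor applications are done in the same way. If controls get no intervention at those two stages, lavender is compared there with nothing rather than with the same routine using plain oil. Any effect of slow breathing or of a nurse's attention would then be credited to lavender.

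The outcomes most exposed are self-rated. Satisfaction with pain control is one of the alternatives in the primary outcome (Section 12), and anxiety is a secondary outcome. Pain is exposed at one point as well. Before surgery, "The level of pain will also be asked prior to application and at the second set of vitals", so this pair of scores straddles the application. Section 12 analyses change scores of pain without saying which change, so the preoperative one may be among them.

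The 45-minute set is a smaller matter. It consists of vital signs, which are not a named outcome, so an imbalance there could act only through extra attention.

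**Working it through.** The plan gives no figure to reproduce on this point, and the sample size does not depend on it. The check compares the text stage by stage and then counts contacts.

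**1. What controls receive, by stage**

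| Stage | Under the same-sequence rule | In the stage's own sentence |
|---|---|---|
| Preoperative wrist | Coconut oil, rubbing, slow breathing | Two sets of measurements, no intervention |
| Recovery-room mask | Coconut oil | Coconut oil, same time intervals |
| Floor wrist, 4-hourly | Coconut oil, rubbing, slow breathing | No intervention |
| Floor vital signs at 45 minutes | Not addressed in terms | Timed from lavender; control timing not stated |

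The preoperative and floor sentences conflict with the rule if taken literally. The recovery-room sentence agrees with it. The 45-minute sentence is silent on controls, whereas the preoperative text gives controls two sets and the recovery-room text gives them the same intervals.

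**2. Wrist applications per full floor day**

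Inputs from Section 9: every 4 hours, from 6am to 9pm. The window is 21 − 6 = 15 hours, and 15 / 4 = 3.75, so a fixed 4-hourly clock has either 3 or 4 slots in it. For example, 6, 10, 14 and 18h give four; 9:30, 13:30 and 17:30 give three. Over all 240 one-minute starting times of such a clock, 75% give four slots and 25% give three.

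**3. Vital-sign sets per full floor day**

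- Routine sets, each arm: 24 / 4 = 6.
- One 45-minute set per wrist application: 3 to 4.
- An arm that has the 45-minute set: 6 + 3 = 9 to 6 + 4 = 10.
- An arm that does not: 6.

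If the nightly cotton ball also counts as an application, add one set per night, assuming it is charged once. These counts are for full 24-hour days. Arrival and discharge days are partial and give fewer, and no total for the stay is claimed.

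**4. What each reading implies**

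- Coconut oil throughout, 45-minute set in both arms: procedures match and nothing is confounded by routine or contact.
- Coconut oil throughout, 45-minute set in the lavender arm only: 3–4 extra vital-sign contacts per full day for lavender patients (9–10 against 6).
- Both sentences literal, 45-minute set in the lavender arm only: the same extra contacts, plus one preoperative breathing exercise and 3–4 per full floor day, against none in controls.

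**The case against.** The strongest reply is that the intended design is clear and only the drafting is loose. Section 4 describes a control without essential oil but with coconut oil, so no intervention can be shorthand for no lavender. The same-sequence rule follows directly on the list that contains both wrist steps, and the literal reading would cancel it at exactly those steps. Section 10 (Risk/Benefit Assessment) tells staff how to remove coconut oil that irritates a control patient's skin. Section 5 excludes coconut allergy, although that is weaker support because the lavender is itself diluted in coconut oil.

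The 45-minute gap has a similar answer. Section 9 also times the preoperative anxiety and sleep questionnaires before the application of lavender. Both arms must complete these, since sleep and anxiety are outcomes. The plan therefore uses the phrase loosely for the study application in either arm, and the 45-minute sentence can be read that way too.

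Most of this stands. It makes the coconut-oil reading the more likely one, and it means that a lavender-only 45-minute set is possible but not shown. It does not remove the conflict. The recovery-room sentence names coconut oil while the sentences on either side of it say no intervention. The preoperative wording excludes any intervention, which is broader than excluding lavender. Section 4 also calls the control the current standard of care, which suits the literal reading. Staff carrying out the floor step would be following the floor sentence.

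**Conclusion.** The inconsistency is real and should be corrected before the procedures are put into use. The intended control is most probably coconut oil applied in the same way, but two operational sentences say otherwise and a third leaves control timing open. Different staff could apply the control differently, and analysis could not repair that.

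On the literal reading, the imbalance is one preoperative breathing exercise plus 3–4 per full floor day, against none. If the 45-minute set is taken in the lavender arm only, there are also 3–4 extra vital-sign contacts per full day. These figures assume a fixed 4-hourly clock and full 24-hour days. They count contacts and do not measure bias, whose size cannot be derived from the documents.

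A reader might infer two stronger points, and the documents support neither:

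- *That controls receive nothing before surgery and on the floor.* The same-sequence rule, Section 4, the recovery-room sentence and the irritation instruction all point the other way.
- *That lavender patients have 9–10 vital-sign sets against 6 however the text is read.* The plan leaves control timing unstated. It does not say that controls go without the set, and on the looser use of the lavender phrase the counts are equal.

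**What to change.** Change three sentences in Section 9:

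- Preoperative: controls have their two sets of vital signs and pain scores *with coconut oil alone applied to the wrist with the same rubbing and one minute of slow breathing*, in place of the words that exclude any intervention.
- Floor: after each 4-hourly set, lavender in the experimental group and *coconut oil alone, applied in the same manner, in the control group*.
- Repeat vital signs: one more set *45 min after each application of the assigned oil, in both arms*.

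Dosing times need not move, and no sets need be dropped.

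The certain cost is the wording. If controls were not already meant to have the 45-minute set, add about 3–4 daytime vital-sign sets per control patient per full day, and one per night if the cotton ball counts as an application. The change matches procedures between arms. It does not mask the scent, so expectation effects on self-rated outcomes would remain.

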The lavender essential oil used will be from the company doTERRA. This essential oil company was chosen because this company has a medical and science governing board made up of physicians, surgeons, chemists and pharmacists. The oil is also third party tested by [name] a trusted chemist in the essential oil community for purity and quality. Gas chromatography and mass spectrometry are used to ensure purity and no unwanted substances are in the essential oil. doTERRA's essential oils have also already been used in a hospital setting at Vanderbilt University hospital in Tennessee. doTERRA's essential oils were diffused in the Vanderbilt ER at the nursing stations. After 3 months of diffusing staff felt less work related stress, less time feeling overwhelmed, and had more energy at work [13].

5. Selection of Subjects:

Potential subjects will be selected from the clinic of [name]. Subjects will be consented by investigators or study key personnel.

Inclusion Criteria:

Women undergoing any form of breast reconstruction therapy Ages 18-85 At least a one night stay in hospital after surgery

Exclusion Criteria:

Sensitivity or allergy to coconut Use of sleeping aide drugs Use of benzodiazepines History of any of the following: asthma, eczema, allergy to flowers, smell disorders Sensitivity to lavender oil or any of its ingredients Pregnant women will be excluded from the study. During routine preoperative testing the patient's menstrual history or urine pregnancy test will be performed to identify any patient who is pregnant.

6. Subject Recruitment & Compensation:

Enrollment goal will be 60 subjects. We anticipate enrolling 60 subjects over 6 months and anticipate the trial to be complete within 1 year. The subjects will not be compensated for the study.

7. **Consent Process** – see Section 14 of the e-IRB submission form and complete the questions in that section.

8. Subject's Capacity to Give Legally Effective Consent:

9. Study Interventions:

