- For coughing or any feeling of shortness of breath or chest discomfort, lavender oil therapy will be stopped. Any lavender applied to the skin will be diluted with fractionated coconut oil as mentioned above.
- For any serious, unexpected event, which occurs to any subject during this study the appropriate DUHS IRB Adverse Event notification will be completed, e-signed by the PI and submitted to the DUHS IRB within 5 days of notification of the reported event.
- Any patient who does not want to participate in the study can decline at any time.
- The patient's demographics including name will remain confidential.

11. Costs to the Subject:

Study intervention and Lavender Oil will be provided to subjects at no additional cost. Subjects and/or their regular insurance provider will be responsible for all procedures and tests considered standard of care for their condition.

12. Data Analysis & Statistical Considerations:

Study Design/Endpoints: The primary outcome will be a difference in pain scores between the 2 groups and/or decrease in narcotic use and/or increased patient satisfaction of pain control. Secondary outcomes are better sleep and decreased anxiety.

Analytic Plan and Method: Differences in the change scores of pain in the two groups as well any other demographic and clinical continuous variables will be examined using t-test or Wilcoxon test, depending on whether the variables are normally or non-normally distributed respectively. The differences between the categorical variables will be examined using chisquared or Fisher's exact test. Analysis will be conducted under the intention to treat (ITT). Missing data will be imputed under multiple imputation methods. Differences in the outcomes while controlling for potential covariates (age, etc) will be examined using linear regression. Significance of the tests will be assessed at alpha = 0.05. Analysis will be conducted using SAS 9.4 (SAS Institute, Inc., Cary, NC.).

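### Narcotic use is a primary outcome, but prior opioid use is not recorded and non-narcotic analgesia is not extracted, which costs precision and leaves a narcotic difference hard to interpret

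*Combined protocol and SAP*

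**What the plan says.** Section 12 (Data Analysis & Statistical Considerations) defines the primary outcome as a "difference in pain scores between the 2 groups and/or decrease in narcotic use and/or increased patient satisfaction of pain control". A narcotic difference alone could therefore be presented as success.

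Section 9 (Study Interventions) describes the analgesic data in three places:
- Surgery: "A review of the electronic medical record will be done to record amount of narcotic needed interop in both groups".
- Recovery room: "The amount of narcotic needed in the recovery room will be taken from the electronic medical record for each group".
- Floor: "There will be a review of narcotic use from the electronic medical record from both groups".

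All three concern narcotics only. No section plans to extract non-opioid analgesics or regional blocks.

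Section 5 (Selection of Subjects) admits "Women undergoing any form of breast reconstruction therapy". Its only exclusions for drug use are "Use of sleeping aide drugs Use of benzodiazepines". Opioid use is not mentioned there, and no section plans to record it at baseline. Section 12 describes the adjusted analysis as "Differences in the outcomes while controlling for potential covariates (age, etc) will be examined using linear regression", so age is the only covariate named. Section 4 (Design) gives 1:1 permuted-block randomisation with 30 patients per arm and states no stratification factor.

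**The concern.** The drug-use exclusions bear on sleep and anxiety, which are secondary outcomes. Nothing comparable is done for prior opioid use, a plausible strong predictor of a primary outcome. The open-ended covariate list does not fill the gap, because a variable that nobody plans to collect cannot be relied on for adjustment.

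Two separate things are at stake:
- **Before allocation.** Prior opioid use adds variance to narcotic totals and may by chance be uneven between arms of 30.
- **After allocation.** Regional blocks and non-opioid drugs can lower narcotic need. Randomisation does not equalise care given once the arm can be recognised. Section 10 lists a pleasing aroma among the benefits of lavender, Section 4 describes the carrier as odorless, Section 9 has the anesthesia team apply the oil during surgery, and no blinding is stated. If co-analgesia differed between arms, in either direction, the narcotic comparison would absorb the difference and the data would not show it.

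**Working it through.** **1. The plan's own figure.** Section 12 gives 15 per group for pain, from 6.45 (SD 2.23) against 4.11 (SD 2.13). The difference is 2.34, the pooled SD is √[(2.23² + 2.13²)/2] = 2.18, and the standardised difference is 1.07. A two-sided t-test at 0.05 with 80% power needs 14.66, so 15 per group; the figure reproduces. It concerns pain only. The plan gives no mean, SD or sample size for narcotic use, so everything below rests on assumptions.

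**2. Share of variance due to prior opioid use.** Assume prevalence p, a multiplier m on narcotic need, and a within-group CV of 50%. With the usual patient's mean set to 1:
- between-group variance B = p(1−p)(m−1)²
- within-group variance W = (1−p)(0.25) + p(0.5m)²
- share = B/(B + W)

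| p | m = 2 | m = 3 |
|---|---|---|
| 5% | 0.0475/0.335 = 14% | 0.19/0.54 = 35% |
| 10% | 0.09/0.415 = 22% | 0.36/0.81 = 44% |
| 20% | 0.16/0.56 = 29% | 0.64/1.29 = 50% |

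**3. Chance imbalance.** Treat the arms as two independent Binomial(30, p) counts. The probability that they differ by 3 or more prior users, in either direction, is 13%, 27% and 42% at p = 5%, 10% and 20%. The probability in the direction that favours lavender is half of that: about 7%, 14% and 21%.

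**4. What such an imbalance does.** Three extra users at m = 3 raise an arm's mean by 3 × (3−1)/30 = 0.20 of the usual amount. At p = 10% the total SD is √0.81 = 0.90, so the shift is 0.20/0.90 = 0.22 SD. The standard error of the difference is 0.90 × √(2/30) = 0.232, so the shift is 0.20/0.232 = 0.86 standard errors. Simulation with lognormal data, CV 50% and no lavender effect gives these false-positive rates:
- 0 against 3 users: about 10% to 11% (t-test), about 7% (Wilcoxon)
- 2 against 5, or 3 against 6: about 4% to 6% with either test

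In a separate simulation at 20% prevalence, with prior use adding 1.0 to 1.5 SD, the unadjusted t-test kept its overall type I error (4.9% and 4.8%). Among the roughly 7.5% of trials with an imbalance of 20 percentage points or more, the rate was 11% to 16%.

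**5. Precision.** At 30 per arm the detectable difference with 80% power is (1.96 + 0.84) × √(2/30) = 0.72 SD. If prior use explains a share R² of the variance, adjustment multiplies this by √(1−R²): 0.69 SD at R² = 10%, 0.56 SD at 40%. For an assumed 30% reduction in narcotic use, with p = 10% to 20% and m = 2 to 3, simulated power is 38% to 66% by t-test, 55% to 74% by Wilcoxon and about 67% to 76% with the indicator in the regression.

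**6. Co-analgesia after allocation.** Assume that uptake differs by 10 to 30 percentage points and that the agent changes narcotic use by 0.5 to 1.0 SD. The spurious difference is the product, from 0.10 × 0.5 = 0.05 SD to 0.30 × 1.0 = 0.30 SD. With standard error √(2/30) = 0.258 SD, the false-positive rate is 1 − Φ(1.96 − shift/0.258) + Φ(−1.96 − shift/0.258), which runs from 5.4% to 21%.

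**The case against.** A reader might infer that a few opioid-tolerant patients would dominate the narcotic comparison or bias it systematically. The documents do not support that. Allocation is randomised, so prior use is balanced in expectation, and step 4 shows that even three extra heavy users usually leave the false-positive rate near nominal. Section 12 also allows a Wilcoxon test for non-normal data, which limits the pull of heavy users and already recovers part of the lost power.

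A reader might also take the background's report of reduced Tylenol use after tonsillectomy as a sign that the outcome was misdirected. The same section cites decreased opioid use in the recovery room after gastric banding, so narcotic use has direct support as an outcome. Nor would a patient who needs less Tylenol necessarily show no benefit, since pain scores and satisfaction are primary components too.

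Further objections are fair. Prevalence, multiplier and CV come from outside the documents. The documents do not say whether home opioids would count in the narcotic total or whether blocks vary at this site. That staff who recognise the arm would change co-analgesia is a possibility, not something the plan states. The word etc leaves the covariate list open, so adjustment is unspecified rather than ruled out.

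What stands after all this: no section plans to collect either kind of data, so the trial could neither adjust for prior use nor show whether co-analgesia was similar between arms.

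**Conclusion.** The point holds as one of precision and interpretability. It is not a claim that the narcotic comparison is invalid.

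For prior opioid use, the overall type I error is intact. Under the assumed 5% to 20% prevalence, 2 to 3 times the narcotic and CV 50%, it explains 14% to 50% of the variance. In the step 5 power scenarios, adjustment gains about 10 to 29 points over the t-test (76 − 66 and 67 − 38) and about 2 to 12 points over Wilcoxon (76 − 74 and 67 − 55), comparing the ends of the ranges.

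Co-analgesia is the more serious part for interpretation, because randomisation does not protect it and no blinding is stated. Its possible effect, 0.05 to 0.30 SD with a false-positive rate of 5.4% to 21%, depends wholly on an assumed difference between arms that the documents neither show nor rule out. The change is worth making before enrolment because it is cheap and the baseline question is best asked before treatment.

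**What to change.** - At consent, record preoperative opioid use as yes or no, with the daily dose if yes. Pre-specify the yes/no indicator as a covariate in the narcotic and pain regressions. The indicator is preferable to a linear dose term, because at 5% to 10% prevalence only 3 to 6 of 60 patients would carry that term, with high leverage.
- In the record review already planned, also extract regional block (yes/no) and the dose of each non-opioid analgesic in both arms. Report these by arm beside narcotic use as descriptive context.
- Do not adjust for analgesia given after randomisation, and do not make a narcotic-sparing claim conditional on it. A rule that non-opioid use must not be higher in the lavender arm, with no margin, would block a real effect about half the time when one agent truly does not differ, and more often with several agents.

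The cost is one question, one covariate and slightly more data abstraction. Eligibility, treatment and recruitment do not change.

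### Section 10 writes Benadryl rescue for a persisting skin reaction into the lavender arm only, does not hold further skin doses, and the plan does not list Benadryl use as data although sleep is an outcome

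*Combined protocol and SAP*

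**What the plan says.** **Rescue.** Section 10 (Risk/Benefit Assessment) treats skin irritation by diluting the essential oil with plain coconut oil, wiping it off, and doing both again. If that fails: "If there is still a reaction and the patient is uncomfortable oral Benadryl will be given, 25mg PO Q6hrs prn itching or skin irritation". The control arm has its own sentence: "In the control arm, should the coconut oil irritate the skin it will be removed using a 4 x 4 cotton swab". It has no drug step.

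**Stopping.** Section 10 stops lavender for coughing, shortness of breath or chest discomfort. It states no stop or hold for a skin reaction. It also says that a patient may decline at any time.

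**Dosing.** Section 9 (Study Interventions) applies oil in surgery "on the temple region over the temporal artery every 2 hours until completion of surgery", with shoulders or feet as alternative sites. On the floor the wrist is dosed every 4 hours between 6am and 9pm. Controls receive coconut oil in the same sequence, and the stated aim is: "This will ensure the same procedures are carried out under both arms".

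**Outcomes and data.** Section 12: "Secondary outcomes are better sleep and decreased anxiety". Section 9: "The sleep questionnaire will be given in preop before application of lavender and then daily for every post-op day they stay". The drug use that Section 9 says it will collect is narcotic use in surgery, in the recovery room and on the floor; for the floor it says: "There will be a review of narcotic use from the electronic medical record from both groups". Section 5 excludes patients on benzodiazepines and also lists: "Use of sleeping aide drugs".

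**The concern.** Two things are at stake.

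The first is the care of a patient whose skin reacts. If the reaction outlasts both dilutions, nothing in Section 10 takes her off the skin-dose schedule. If it starts after the preoperative wrist dose, the next skin doses come under anesthesia.

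The second is the sleep comparison. The entry criteria keep out patients who use sleep aids or benzodiazepines, yet a sedating drug is then written into one arm's procedure after randomization. Its trigger is a reaction to lavender, so randomization does not balance its use. Because it is not a listed data item, a reader of the results could not tell how many patients received it, in which arm, or near which sleep score.

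**Working it through.** The plan has no figure of its own on this point. The check has two parts: the text side by side, then a range for the possible effect on the sleep comparison.

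**Text**

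| Item | Lavender arm | Control arm |
|---|---|---|
| First response to irritation | Dilute and wipe, twice | Remove the oil |
| Persisting, uncomfortable reaction | Oral Benadryl as needed | Nothing stated |
| Hold on later skin doses | None stated | None stated |
| Benadryl use as a data item | Not listed | Not listed |

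**Exposure as written**

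- Benadryl ceiling: 24 h / 6 h = 4 doses; 4 × 25 mg = 100 mg per day. This is the limit of an as-needed order, not expected use.
- Wrist doses on a full floor day: for example 6, 10, 14 and 18 h, so 4. Over the typical stay of 1-3 days that is 4 to 12 if all are full floor days, and fewer in practice because the surgery and discharge days are partial.

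**Possible effect on the sleep comparison**

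Inputs:

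- 30 patients per arm (Section 4) and alpha 0.05 (Section 12), taken as two-sided.
- The documents give no rate of persisting reactions and no effect of Benadryl on sleep, so both are assumed. *k* of the 30 lavender patients are treated and no controls. Each treated patient's sleep score moves by a net *d* SD, reaction and drug together.

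Formulas:

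- Shift in the lavender mean = *k* × *d* / 30.
- Standard error of the arm difference = √(2/30) = 0.258 SD.
- Chance of a falsely significant lavender benefit = upper-tail rejection of a t-test with 58 degrees of freedom, by noncentral t with noncentrality shift / 0.258 and no true lavender effect. With no shift it is 2.5%.

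| *k* | *d* (SD) | Shift (SD) | Chance of false benefit |
|---|---|---|---|
| 3 | −0.5 | −0.05 | 1.6% |
| 1 | +0.25 | 0.008 | 2.7% |
| 3 | +0.5 | 0.05 | 3.8% |
| 6 | +0.5 | 0.10 | 5.7% |
| 6 | +1.0 | 0.20 | 11.5% |

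For scale, 30 per arm gives 80% power to detect a difference of about 0.74 SD. A shift of 0.05 SD is about 7% of that (0.05 / 0.74).

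The range has to span zero. Benadryl is given only to a patient who still has a reaction and is uncomfortable, so every recipient carries something that may disturb sleep alongside a drug that may help it. The last row needs one lavender patient in five to have a reaction that survives two dilutions, and a full SD of sleep gain in each. Section 9 expects irritation to be unlikely at this dilution, which makes the rows with small *k* the more plausible ones.

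**The case against.** A reader might infer that this rule biases the sleep result in favor of lavender. The documents do not support that: the net direction is unknown, and a net harm to sleep lowers the chance of a false benefit. The 11.5% is an extreme corner of an assumed range.

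A reader might also infer that control patients are barred from Benadryl, or that its use would leave no trace. Neither follows. The control sentence does not forbid it and usual care could supply it. Doses would be in the medical record, Section 13 sends adverse events to a committee, and Section 12 leaves its covariate list open. What stands is narrower: the written rules differ by arm, and no listed data item captures the drug for analysis.

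A fair statistical objection is that treating a reaction caused by lavender is a consequence of being assigned to lavender, so the intention-to-treat comparison properly includes it. I accept this, and the main analysis should not change. It does not remove the need to know how much rescue was given in each arm.

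On safety, an awake patient can refuse the next dose, and the anesthesia case needs a reaction shortly before or during surgery. Both are true. But under anesthesia refusal is not available, and elsewhere the schedule should not depend on the patient to stop it. The committee's planned safety meeting is at half recruitment, so it does not guide care at the bedside.

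**Conclusion.** The point holds as a minor design weakness worth correcting. Followed as written, the plan keeps a reacting patient on skin doses, possibly under anesthesia, and gives the two arms different written rescue for the same problem. That part rests on the text alone.

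The effect on results is probably small and concerns mainly the secondary sleep outcome: a shift of 0.05 SD or less in either direction if at most 3 of 30 lavender patients are treated and each moves by 0.5 SD. Those two figures are assumptions, and that Benadryl is sedating is general drug knowledge. The stronger reading, that the rule favors lavender on sleep, is not established. What can be said is that the planned data would not let anyone check.

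**What to change.** 1. **Hold (Section 10).** In either arm, make no further application to an irritated site. If the reaction persists after removal, withhold all skin applications, and mask oil if the face is affected, until a clinician has reviewed the patient and recorded whether to resume.
2. **One drug rescue rule (Section 10).** Apply the same rule in both arms, with a non-sedating antihistamine preferred where the clinician finds it suitable and Benadryl still available.
3. **Recording (Sections 9 and 12).** Extract antihistamine drug, dose and time in the record review already planned for narcotics, and report use by arm. Intention to treat stays as it is.

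Leave the two-step coconut-oil dilution as written. I would not add an analysis that sets sleep scores near a Benadryl dose to missing: with daily scores and a stay of 1-3 days, it could erase a patient's only postoperative score.

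The cost is a few sentences, a little more record review, and a few missed lavender doses in patients who react. No visits or patients are added.
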